4. If the start date is completely missing, but the AE is either ongoing or the stop date is after the first date of drug application, then impute the start date as the first date of study drug application.
5. If using the above rules, the stop date is before the start date, then leave the stop date missing and assume that AE is treatment-emergent for the purpose of the analysis.

Completely missing stop dates will not be imputed. The partial stop dates will be imputed as follows:

1. If the year is missing, the stop date will not be imputed.
2. If the month is missing, then the month will be imputed as December.
3. If the day is missing, then the day will be imputed as the last day of the month.

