8.7.2. Adverse Events by Preferred Term and System Organ Class

For the first interim analysis serious AEs will be mapped to system organ class (SOC) and preferred terms (PTs) using the 19.1 version of MedDRA.

If there is a gap between the completion of the study SD-005 and the start of the study SD-006, adverse events starting after the last study day or changing the severity or relationship to treatment within the gap will be counted as medical history for the extension study SD-006. Continuing adverse events will also be captured in medical history for the extension study SD-006. If the severity or relationship to treatment changed on or after the first dose of study medication, then that AE is considered a TEAE after that change.

If an AE started after signing an informed consent/assent but before the first dose of study medication was taken in the study SD-006, then such an AE is non treatment-emergent.

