8.7.4. Missing AE Onset, Severity, and Relationship

8.7.4.1. Missing or Partial AE Dates

The following list describes how partially missing date information will be handled as it relates to partial or missing start dates. Partial dates will be imputed as follows

1. If year is not missing and is after the year of first application of study drug:
 - a. If Month is missing, then Month will be imputed as January.
 - b. If Day is missing, then Day will be imputed as the first of the month.
3. If year is not missing and is the same as the year of the first application of study drug:
 - a. If Month is missing, then impute the Month as the month of the first application of study drug.
 - b. If Day is missing but Month is on or after the month of first application of study drug, then impute Day as the first day of the month.

- c. If the Day and Month are missing then impute Day and Month as the Day and Month of the first study drug application.
4. If year is missing, then impute the year as the year of the first study drug application:
 - a. If Month is missing, then impute the Month as the Month of the first study drug application.
 - b. If Day is missing, then impute the Day as the day of the first study drug application.
5. If the start date is completely missing, but the AE is either ongoing or the stop date is after the first date of drug application, then impute the start date as the first date of study drug application.
6. If using the above rules, the stop date is before the start date, then leave the stop date missing and assume that AE is treatment-emergent for the purpose of the analysis.

Completely missing stop dates will not be imputed. The partial stop dates will be imputed as follows:

1. If the year is missing, the stop date will not be imputed.
2. If the month is missing, then the month will be imputed as December.
7. If the day is missing, then the day will be imputed as the last day of the month.

Imputed dates will be flagged in the individual supportive patient listings.

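### The SAP's date-conflict rule counts as treatment-emergent some adverse events whose stop date shows that they ended before first application, and imputed stop dates have no upper limit

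*SAP*

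**What the plan says.** SAP 8.7.4.1 gives the rules for partial adverse event dates, and SAP 6.5.2 repeats them with different item numbers. Item numbers below are those of 8.7.4.1.

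- **Start year later than the year of first application (item 1):** "If Month is missing, then Month will be imputed as January" and "If Day is missing, then Day will be imputed as the first of the month".
- **Start year equal to the year of first application (item 3):** with only the day missing, "If Day is missing but Month is on or after the month of first application of study drug, then impute Day as the first day" in that month. With both missing, "If the Day and Month are missing then impute Day and Month as the Day and Month of the first study drug application".
- **Start year missing (item 4):** the year of first application is used, with its month and day wherever those are missing too.
- **Start wholly missing (item 5):** the start is set to first application, but only if the event is ongoing or stopped after that date.
- **Start later than stop after these steps (item 6):** "the stop date is before the start date, then leave the stop date missing and assume that AE is treatment-emergent". Item 5 of SAP 6.5.2 opens in the same way: "If using the above rules, the stop date is before the start date, then leave the stop date missing".
- **Partial stop dates:** these take the latest possible value. "If the month is missing, then the month will be imputed as December", and a missing day becomes the last of the month. No upper limit is given.

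SAP 8.7.2 addresses an event that begins after consent but before the first SD-006 dose: "then such an AE is non treatment-emergent". SAP 8.7.3 puts such events in a listing only, and calculates the listed duration from the resolution and onset dates.

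**The concern.** Treating an event as treatment-emergent when its timing is unknown is a usual and cautious convention. Item 6 goes further. In its main case the start was set to first application only because nothing better was known, while the stop date is either recorded or already at its latest possible value. When the two conflict, the rule keeps the invented date and drops the informative one.

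Safety is the primary endpoint (Protocol 9.2) and the treatment-emergent tables are its main output. A rule that moves pre-dose events into those tables contradicts the SAP's own classification. The absence of a cap on imputed stop dates is a separate defect in the same section. It can give resolution dates well after anyone was observed.

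**Working it through.** The plan states no figure here, so the check is a reading of the rules, confirmed by enumeration.

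**Notation.** F is the date of first application. A is the imputed start. S is the stop date, recorded or imputed to its latest possible value. Item 6 applies when S < A. The true start is never later than the true stop, and the true stop is never later than S.

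**When item 6 can apply, for the ordinary patterns**

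| Start components missing | A | S < A possible? |
|---|---|---|
| Day only | 1st of the month | No: A is on or before the true start |
| Day and month, year after F's year | 1 January | No, same reason |
| Day and month, F's year (item 3c) | F | Only if S < F |
| All, item 5 applied | F only if ongoing or S > F | No |
| All, item 4 applied | F | Only if S < F |

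If S < F, then true start ≤ true stop ≤ S < F. The event began and ended before dosing, so under SAP 8.7.2 it is not treatment-emergent. Item 6 says that it is.

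**Enumeration.** The rules were applied to six choices of F, every true start date from the year before F's year to the year after it, selected durations from 0 to 400 days, and full and partial stop dates.

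- Day only missing: 0 conflicts.
- Day and month missing, later year: 0 conflicts.
- Day and month missing, F's year: 23,203 conflicts, all ending before F. If items 3a and 3b are applied in turn instead of 3c, A is the first of F's month. That gives 21,946 conflicts, again all ending before F.
- All missing: 0 conflicts under item 5; 128,797 under item 4, all ending before F.

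These counts show which cases can occur, not how often they would.

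**Illustration of the main case.** Let F be 15 June 2016, with a start recorded as 2016 only and a stop of 14 June 2016. Then A is 15 June 2016 and S < A. The stop is blanked and the event is counted as treatment-emergent, although it ended one day before F (15 − 14 = 1).

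**Unusual patterns.** With the year and day missing but the month known, item 4 supplies F's year and F's day. Take the same F and an event that truly ran from 5 to 10 September 2016, with only the month of its start recorded. A becomes 15 September 2016, after the stop of 10 September. This event is genuinely treatment-emergent, so item 6 classes it correctly but still loses its stop date. With the month alone missing, an event that truly ran from 20 May to 18 June 2016 gets A = 20 June 2016. It began before F, ended after F, and also triggers item 6.

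**Reach.** Study day 0 is the consent date at Visit 1 (SAP 6.2.1), and cream is dispensed at that visit (SAP Table 1). Adverse events are collected from consent. SD-005 events and events in the gap between studies go to medical history (Protocol 13.3, SAP 8.7.2). The exposed interval is therefore consent to F. If F is the consent date, no correctly recorded adverse event can stop before F, and the ordinary patterns never trigger item 6.

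**Uncapped stop dates.** A stop recorded as 2018 becomes 31 December 2018. The letter halting applications is dated 4 June 2018 (SAP 5.1). June to December gives 26 + 31 + 31 + 30 + 31 + 30 + 31 = 210 days. Protocol 13.3 follows adverse events for 30 days after the last dose. Counting those days from 4 June, the overshoot is 210 − 30 = 180 days.

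**The case against.** The strongest reply is that the set is nearly empty and the error is on the cautious side. An affected event must usually start and end between consent and first application, and also lack the month of its start. The study is open-label with no comparison between groups, and over-counting treatment-emergent events is less harmful than missing them. All of this stands, and it limits the point to a small correction.

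It can also be said that item 6 applies only for the purpose of the analysis, that imputed dates are flagged in the listings, and that outcome is a separate field. This stands in part. A reader might infer that these events would be reported as ongoing on drug with wrong durations. The documents do not support that: a blank resolution date is not an outcome of ongoing, and the duration becomes uncomputable, not wrong. However, the flagging sentence covers imputed dates and does not clearly cover a stop date that was removed.

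Another reply is that leaving a stop date missing might refer only to partial stops. The classification is still wrong on that reading. A partial stop takes its latest possible value, and if even that is before F, the event ended before dosing.

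Finally, SAP 6.5.2 loosely describes everything collected after consent as treatment-emergent. SAP 8.7.2 draws the line at first dose explicitly, and 8.7.3 relies on it by listing non-treatment-emergent events separately, so this does not rescue item 6.

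**Conclusion.** Item 6 is wrong as written for a year-only start in the year of first application. There it can act only on events that ended before dosing, and it classes them against SAP 8.7.2. For a wholly missing start the error depends on whether item 4 or item 5 governs. The SAP does not say which, although item 5 is the more specific.

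The numerical effect is probably very small. The documents give no count of affected events and no interval between consent and first application, so no rate can be stated.

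Three stronger readings are not supported:

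- **That item 6 only ever catches pre-dose events.** This holds for the ordinary patterns, but not when the month alone is missing or the year is missing with the month or day known.
- **That the safety tables are materially inflated.** Collection from consent and the transfer of earlier events to medical history rule out most of the cases in the enumeration.
- **That 210 days bounds the error in duration.** It is the overshoot past the letter of 4 June 2018. Patients still returned for an end-of-study visit, and events leading to withdrawal may be followed longer. The imputation error itself can be larger: a true stop of 5 January 2018 recorded as 2018 moves by 365 − 5 = 360 days. A date after death is possible under the rules, but nothing in the documents shows that it occurred.

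**What to change.** Replace item 6 of SAP 8.7.4.1 and item 5 of SAP 6.5.2 with wording to this effect:

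> An imputed start date is never later than the recorded or imputed stop date; if it would be, set the start to the stop date and keep the stop date. If the stop date (or its latest possible value) is before first application, the AE is not treatment-emergent; otherwise, where the start is uncertain, assume it is treatment-emergent. Cap every imputed stop date at the earliest of death, last contact and data cut-off.

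The first sentence must cover every missing pattern. A rule limited to stops before first application would leave the September case above with a stop before its start and nothing to resolve it. State also which of items 4 and 5 (items 3 and 4 in 6.5.2) applies to a wholly missing start, and apply the cap before comparing start with stop.

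The cost is a few sentences and minor programming. The count of treatment-emergent events may fall slightly. Where the start is moved to the stop, the listed duration becomes one day (stop − start + 1 = 1), so the existing flag for imputed dates should appear beside it.

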8.7.4.2. Missing Severity

If severity is missing for any AE, then its severity will be classified as missing in the summary tables.

8.7.4.3. Missing Relationship

If the assessment of relationship of the AE to study treatment is missing for any AE, then it will be presented as missing in the listings and in the summary tables.

8.7.5. Summaries of Adverse Incidence Rates for Serious Adverse Events (SAE), Adverse Event Dropouts, and Death

During the treatment period, the number and percentage of patients who experienced TESAEs and separately TEAEs leading to withdrawal from the study will be presented by SOC and by PT within each SOC for each treatment. Treatment-emergent SAEs and separately TEAEs resulting in withdrawal from the study will be similarly presented by severity (mild, moderate, severe), by relationship to study drug (related would include definite, probable, and possible) and by outcome of events. Additionally the number of TESAEs (as opposed to the number and percentage of patients) and separately TEAEs leading to withdrawal will be presented.

Number of patients with TESAEs and separately TEAEs resulting in withdrawal as well as number of TESAEs and separately the number of TEAEs leading to withdrawal will also be presented by the following subgroups of Age (28 days to <2 years, 2 years to <12 years, 12 years to <=18 years, >18 years), EB type and independently. Subgroups for age are defined based at the patient's age at Baseline.

In case that there are non-treatment emergent serious adverse events, they will be listed.

A listing of all serious adverse events and discontinuations due to AEs will be included. Patient with deaths, SAEs or patients who withdraw due to AE will be listed separately and discussed with patient narratives.

8.7.6. Discontinuation from the Study

Number of patients who discontinued from the study and reasons for discontinuation will be summarized.

8.7.7. Clinical Laboratory Evaluations

Pregnancy test results will be listed for all female patients of child bearing potential only.

8.7.8. Other Observations Related to Safety

8.7.8.1. Vital Signs

Vital Signs (weight, height/length and temperature) conducted under the physical examination will be summarized using descriptive statistics for both actual results and change from baseline for each treatment group. Vital Signs assessments will also be presented in a listing. All vital signs will be presented metric units.

8.7.8.2. Physical Findings

Physical examination findings will be summarized in shift tables that will be presented to display the shift in the normal range categories (normal vs. abnormal) from baseline to the final evaluation. Baseline is defined in section [6.3](#).

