5. BACKGROUND INFORMATION

Epidermolysis Bullosa (EB) is a rare group of inherited disorders that typically manifest at birth as blistering and lesion formation on the skin and, in some cases, the epithelial lining of other organs, in response to little or no apparent trauma. In consequence, the skin is extremely fragile which can result in shearing of the skin, causing a high risk of infection. All forms of EB are both debilitating and life threatening (see Appendix 1 Epidermolysis Bullosa Subtypes). In some EB subtypes, high mortality occurs before the age of 1 (Junctional Herlitz), and others in adolescences to early adulthood, typically due to infection or failure to thrive. In addition, children surviving into their 20's and 30's are also at risk for development of a virulent form of squamous cell carcinoma, which is in many cases fatal.

There are no standard of care products available to treat the dermal manifestations of EB, and there is no approved drug for EB in either Europe or the United States. There have been numerous studies published on potential treatments for skin manifestations associated with EB, including vitamin E therapy, systemic phenytoin, topical nonsteroidal agents, cyproheptadine, tetracycline, and dapsone. No controlled studies showed clinical benefit of any therapy. Newer exploratory treatments including skin grafts, bioengineered skin products, and gene therapy have been unsuccessful to date.

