9. STUDY DESIGN AND ENDPOINTS

9.1. Study Design

This is an open label, multi-center extension study to assess the long-term safety of ZORBLISA in treating patients with Simplex, Recessive Dystrophic, and Junctional non-Herlitz Epidermolysis Bullosa. All patients must have completed SD-005 to be eligible to participate in this open label extension.

ZORBLISA will be applied topically, once a day, to the entire body for a period of 1440 days. Patients will return to the study site at Month 1, then once every 3 months until Month 48 (Months 3, 6, 9, 12, 15, 18, 21, 24, 27, 30, 33, 36, 39, 42, 45, and 48).

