9.2. Primary Endpoint

The primary endpoint is the long-term safety of ZORBLISA in patients with Simplex, Recessive Dystrophic, and Junctional non-Herlitz Epidermolysis Bullosa. Safety is assessed via monitoring of local tolerability at the application sites, occurrence of adverse events and physical examinations.

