9.3.1.1. Definition of Lesional Skin for Assessment and Calculation of BSA Coverage

- Consists of area(s) that could contain any of the following: blisters, erosions, ulcerations, scabbing, bullae, and eschars, as well as areas that are weeping, sloughing, oozing, crusted, and denuded.
 - Percent of this area recorded for each defined body region (number from 0-100% assigned for each region) BSA

Note: Coloration should not lead to misinterpretation of whether a lesion is active. Erythema and hyper- or hypo-pigmentation do not necessarily indicate that a lesion is active, and in fact can be found in healed or scarred skin that would not be added to BSAI calculation of lesional skin coverage, unless it meets the definition above.

• Other areas categorized as skin that is either healed or scarred are not considered lesional skin.

Figure 9-1: BSAI of Lesional Skin Calculation Charts

(Check only one box and complete the appropriate sections for each region)								
1 🗆 Ag	1							
Column 1	Column 2	Column 3	Column 4	Column 5				
Region Number	Region Description	Regional BSA % that is affected*	Weighting Factor	Total BSA % that is affected **				
1	Head / Neck		x .2					
2	Upper Limbs		x .2					
3	Trunk (includes groin)		x .3					
4	Lower Limbs		x .3					
			TOTAL					

2 🗆 Age 8 years or greater

Column 1	Column 2	Column 3 Column 4		Column 5
Region Number	Region Description	Regional BSA % that is affected*	Weighting Factor	Total BSA % that is affected **
1	Head / Neck		x .1	
2	Upper Limbs		x .2	
3	Trunk (includes groin)		x .3	
4	Lower Limbs		x .4	
·			TOTAL	

* For each region, enter the % of BSA that is affected with lesional skin. Score each region separately from 0% - 100%.

** Multiply the value in Column 3 by the factor in Column 4. The Total value at the bottom of the table is the sum of Column 5 values for each region.

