13.1. Physical Examination including Height, Weight, and Temperature

The physical examination performed at the final visit for SD-005 will be utilized as the baseline assessment for SD-006 unless Visit 1 is \geq 14 days after the final SD-005 visit, in which case a physical examination will be repeated An additional physical examination will be done by a physician at Visit 18. The following sites will be examined: head, eyes, ears, nose, throat, neck, chest, lungs, heart, abdomen, skin, and lymph nodes; and the following systems will be assessed: musculoskeletal and neurological. Weight, height, and temperature will be recorded.

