3. STUDY OBJECTIVE

The primary objective is to demonstrate the long-term safety of SD-101-6.0 in patients with Simplex, Recessive Dystrophic, and Junctional non-Herlitz epidermolysis bullosa.

The secondary objectives are to assess the efficacy of SD-101-6.0 in terms of the change in Body Surface Area Index (BSAI) of lesional skin and BSAI of wound burden; as well as assessment of healing of unhealed target wounds in patients rolling over from the SD-005 study.

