8.4. Demographic and Other Baseline Characteristics

Descriptive summaries of demographic and baseline characteristics will be presented for the ITT Population.

Continuous variables such as patient age, weight, height, body mass index (BMI), BSAI (for lesion and wound burden), and temperature will be summarized as described previously. Categorical variables such as patient gender, , age group (28 days to <2 years, 2 years to <12 years, 12 years to < 18years, 18 years to < 65 years, 65 years to <85 years, >=85 years), EB type, and baseline target wound size (=0, >0) will be summarized using number of observations and percentages for each category.

Enrollment by country will be summarized.

Medical history, including disease history will be summarized and listed.

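### Physical examination findings are analysed only as a normal/abnormal shift, so for patients whose skin is rated abnormal at baseline, probably most of them, the table cannot show a new or worse skin finding

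*SAP*

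**What the plan says.** Protocol 9.2 defines the primary endpoint as long-term safety and names three components: "Safety is assessed via monitoring of local tolerability at the application sites, occurrence of adverse events and physical examinations". The examined sites in Protocol 13.1 are "head, eyes, ears, nose, throat, neck, chest, lungs, heart, abdomen, skin, and lymph nodes", plus two body systems. Skin is therefore an examination item, and it is also where the product goes: "ZORBLISA will be applied topically, once a day, to the entire body for a period of 1440 days" (Protocol 9.1).

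The schedule in Protocol 11 and SAP Table 1 places the examination at baseline and at Visit 18 or early termination only. Baseline is normally the SD-005 final examination.

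SAP 8.7.8.2 gives the whole analysis of the findings: shift tables that "display the shift in the normal range categories (normal vs. abnormal) from baseline to the final evaluation". It states no severity grade, no category for worsening and no listing. SAP 8.7.8.1, by contrast, plans a listing for vital signs.

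**The concern.** A two-category shift can record deterioration only in someone who starts in the normal category. The study population is "patients with Simplex, Recessive Dystrophic, and Junctional non-Herlitz epidermolysis bullosa" (SAP 3), and the disorders "typically manifest at birth as blistering and lesion formation on the skin" (Protocol 5). These patients have just finished a trial built around a target wound. For a patient rated abnormal on skin at baseline, the only possible entries are abnormal-to-abnormal and abnormal-to-normal, that is, unchanged or improved. A stable patient and one with a new rash fall in the same cell.

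At stake is how one component of the primary endpoint is read at the drug's application site. A skin row with few or no shifts to abnormal could be taken as evidence of safety when few patients were able to shift. This matters more because SAP 5.1 reports that the product may have been adulterated and that patients were recalled for an end-of-study visit, where the examination is scheduled. The medical review in SAP 6.5.2 covers adverse events. A skin finding noted at that visit but not reported as an adverse event would reach neither that review nor, if baseline skin was abnormal, the shift table.

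**Working it through.** The plan states no figure for this analysis, so there is nothing to reproduce. The 150 patients in SAP 4.4 are an expected roll-over number, not the result of a power calculation.

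**Inputs**
- N = 150 (SAP 4.4). All are taken to have a final examination (assumption).
- p = share rated abnormal on skin at baseline. Not in the documents; range 80% to 100% assumed.
- q = share of patients with a new or worse skin finding at the final examination. Not in the documents; 2%, 5% and 10% assumed.
- New findings are assumed unrelated to the baseline rating.
- The shift is assumed to be shown by body site, which SAP 8.7.8.2 does not say. A single overall rating would be affected more, since abnormal skin alone would make it abnormal.

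**Formulas**
- Patients able to shift from normal to abnormal: m = N × (1 − p).
- Expected findings visible: m × q, out of N × q expected to occur.
- Expected share hidden: 1 − (m × q)/(N × q) = p, whatever the value of q.
- Chance that the table shows at least one: 1 − (1 − q)^m.

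**Results**

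| p | m | Visible at q = 5% (of 7.5) | Chance of at least one, q = 2% | q = 5% | q = 10% |
|---|---|---|---|---|---|
| 0% (reference) | 150 | 7.5 | 95.2% | >99.9% | >99.9% |
| 80% | 30 | 1.5 | 45.5% | 78.5% | 95.8% |
| 90% | 15 | 0.75 | 26.1% | 53.7% | 79.4% |
| 95% | 8 (7.5 rounded) | 0.4 | 14.9% | 33.7% | 57.0% |
| 98% | 3 | 0.15 | 5.9% | 14.3% | 27.1% |
| 100% | 0 | 0 | 0% | 0% | 0% |

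At q = 10%, 15 findings are expected, and the expected visible numbers are 3.0, 1.5, 0.8, 0.3 and 0 for p from 80% to 100%.

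These are expected values, and the observed count will vary. With m = 8 and q = 10%, the chance of two or more visible shifts is 1 − 0.9^8 − 8 × 0.1 × 0.9^7 = 1 − 0.430 − 0.383 = 0.187, about 19%.

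**The other routes, side by side**
- Adverse events. Protocol 13.3.1 treats rash as a reaction and requires clinically relevant worsening to be reported if it meets the adverse event definition; SAP 8.7.3 tabulates the events. The same protocol section says that disease changes may not qualify as adverse events, and it leaves skin site changes captured at the skin site evaluations out of the adverse drug reaction definition.
- Lesional skin extent (BSAI). This is analysed by visit as efficacy (SAP 8.6.1). Protocol 9.3.1.1 does not count erythema or pigment change by itself, so a rash without lesions need not register.
- Skin examination at each visit. Protocol 8.4 calls for it, but it has no row in the schedule and no analysis in the SAP.
- Local tolerability. This is another named component of the primary endpoint, and the SAP has no dedicated analysis of it.

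**The case against.** A reader might infer that every patient has abnormal skin at baseline, so that the table can show nothing. The documents do not support that. They give no share and no rule for rating EB skin at the examination. SAP 8.4 has a baseline category for a target wound of size zero. Protocol 9.3.1.1 says "Other areas categorized as skin that is either healed or scarred are not considered lesional skin", although that definition serves the BSAI only. Appendix 1 describes the most common simplex form as localised and healing without scars. An examiner might also mark as abnormal only what goes beyond known disease. This objection stands: the table is wholly blind only at p = 100%. It does not remove the problem, because one closed target wound does not make the whole skin normal, and without a rating rule sites may rate the same skin differently.

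A reader might also infer that the examination analysis fails throughout, or that skin harm would go unseen. Neither follows. Heart, lungs, abdomen and lymph nodes are examined, and nothing suggests that the shift fails for them; Appendix 1 gives no frequencies by body site. Adverse events are monitored at every visit, and exacerbation of a pre-existing condition falls within the definition. The exclusion of skin site changes limits classification as a drug reaction, not recording as an adverse event. This also stands, subject to the limits of each route shown above.

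Finally, a full shift table shows its abnormal-to-abnormal count, so a careful reader could see the ceiling. That reader still could not tell stable patients from worse ones within that cell.

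**Conclusion.** The point holds in a limited form. In patients rated abnormal on skin at baseline, the planned table cannot show a new or worse skin finding. These are likely to be most patients, by inference from an all-EB population from a target-wound trial. If new findings are unrelated to the baseline rating, the expected share hidden equals the share abnormal at baseline: four in five at 80%, all at 100%. If patients with abnormal baseline skin are more prone to new findings, the hidden share is larger; if less prone, smaller. The range for p and the values of q are assumptions.

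This is a flaw in one descriptive display of a primary-endpoint component, not a total loss of skin safety data. It affects no sample size or error rate. It deserves correction because the affected item is the application site, the other routes are incomplete and the remedy is cheap.

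**What to change.** In SAP 8.7.8.2:

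1. Keep the shift table.
2. Add a by-patient listing of abnormal findings at the baseline and final examinations, by body site.
3. Where descriptive findings were recorded, add for skin at least a category for patients abnormal at baseline with a new or worsened finding at the final examination. Derive it before database lock, under a written rule, without reference to prior-treatment group, and within the medical review already planned in SAP 6.5.2.
4. Tabulate that category by prior-treatment group and overall, and query any new or worsened finding that has no matching adverse event.
5. If descriptive text was not captured, print beside the table the number of patients normal at baseline for each site, so that an absence of shifts is not read as evidence of safety.

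The cost is SAP wording, one listing and a medical read of two examinations for up to about 150 patients, with no new visits or procedures. Calling a finding worsened takes some judgement in an open-label study, and the two examinations may be years apart. Protocol 17.5 requires examination results in the patient file, but the documents do not show that the eCRF holds descriptive text. If it does not, steps 3 and 4 would mean extracting it from the files at greater cost, and step 5 is the fallback.
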